**9.4 Gender and Minority Accrual Estimates**

The gender and minority distribution of the study population is expected to be:

Accrual Targets			
Ethnic Category	Sex/Gender		
	Females	Males	Total
Hispanic or Latino	58	52	110
Not Hispanic or Latino	226	239	465
Ethnic Category: Total of all subjects	284	291	*575
Racial Category			
American Indian or Alaskan Native	2	1	3
Asian	17	14	31
Black or African American	39	34	73
Native Hawaiian or other Pacific Islander	0	1	1
White	226	241	467
Racial Category: Total of all subjects	284	291	*575

\* These totals must agree.

This distribution was derived from AAML0531 and AAML00P2.

## 10.0 EVALUATION CRITERIA

### 10.1 Common Terminology Criteria for Adverse Events (CTCAE)

This study will utilize version 4 of the CTCAE of the National Cancer Institute (NCI) for toxicity and performance reporting. A copy of the CTCAE version 4 can be downloaded from the NCI website at: [http://ctep.cancer.gov/protocolDevelopment/electronic\\_applications/ctc.htm](http://ctep.cancer.gov/protocolDevelopment/electronic_applications/ctc.htm). Additionally, toxicities are to be reported on the appropriate case report forms.

### 10.2 IFI Checklist and Central Review

Institutions will be provided with case report forms to complete which will help to identify whether patients had IFI (IFI checklist). Biopsy and imaging reports are requested rather than report interpretation in order to minimize the work load for sites. An independent data review committee including infectious disease and oncology experts who are unaware of treatment assignments will review and classify all cases of proven/probable IFI by EORTC/MSG.

The following materials in the IFI checklist will be submitted (via the Document Imaging System: [contact]) at the end of each course of protocol therapy, only if they were performed to investigate an IFI according to local physician discretion:

- Pathology reports (including autopsy reports),
- CT scan and MRI reports,
- Fungal Gram stain and microbiology culture results (including both positive and negative results),
- Non-culture mycology testing results (i.e. Histoplasma urine antigens, cryptococcal CSF and serum antigens),
- Ophthalmology exams (even if evidence of fungi not seen), and
- Bronchoscopy reports (even if evidence of fungi not seen).

In addition, dosing and duration of steroid exposure will be collected and entered via eRDE. All reviewers will be blinded to the patient's antifungal exposures in order to limit any bias in determining the primary and secondary endpoints.

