**7.0 EVALUATIONS/MATERIAL AND DATA TO BE ACCESSIONED**

Timing of protocol therapy administration, response assessment studies, and surgical interventions are based on schedules derived from the experimental design or on established standards of care. Minor unavoidable departures (up to 72 hours) from protocol directed therapy and/or disease evaluations (and up to 1 week for surgery) for valid clinical, patient and family logistical, or facility, procedure and/or anesthesia scheduling issues are acceptable per COG administrative Policy 5.14 (except where explicitly prohibited within the protocol).

All baseline studies must be performed prior to starting protocol therapy unless otherwise indicated below.

**7.1 Required and Optional Clinical, Laboratory and Disease Evaluations  
Obtain prior to start of phase unless otherwise indicated.**

STUDIES TO BE OBTAINED	Baseline	Course 1 #	Subsequent Courses #	End of ACCL0933 Therapy
REQUIRED				
History	X			
Physical Exam (Ht, Wt, BSA)	X			
CBC, differential, platelets	X	X	X	X
Creatinine, SGPT, SGOT, bilirubin	X	X	X	X
IFI checklist		X*	X*	X*
OPTIONAL				
Sample for SNP Genotyping		X %		
GM, BG Assays		2x weekly @	2x weekly @	

# Course 1 of fluconazole or caspofungin follows Course 1 of AML therapy. *Subsequent Courses* refers to protocol-directed antifungal prophylaxis, not AML therapy.

\* Submit relevant IFI checklist documents via the Document Imaging System: [contact] at the end of each course of protocol therapy. See Section 10.2 for further details.

% Obtain at end of Course 1, optimally when the patient has ANC > 1000/ $\mu$ L and no circulating blasts.

@ Collect specimens twice weekly during the period of neutropenia (until ANC > 100-500/ $\mu$ L). See Section 13.1 for specimen collection details. It is suggested that specimens be obtained on Mondays and Thursdays but other days are acceptable if more convenient. A minimum of 2 days should separate each specimen collection. All specimens must be collected in the specimen vials provided by MiraVista Laboratories in the shipped lab collection kits. Alternative specimen vials should never be used as they may contribute to false results.

**This table only includes evaluations necessary to answer the primary and secondary aims. Obtain other studies as indicated for good clinical care.**

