## 9.0 STATISTICAL CONSIDERATIONS

### 9.1 Statistical Design

This is a randomized open-label trial to determine if prophylaxis with caspofungin during periods of neutropenia following chemotherapy for AML is associated with a lower incidence of proven or probable IFI compared with fluconazole. Eligible AML patients at ages 3 months to 30 years will be randomized to receive daily prophylaxis with either caspofungin or fluconazole. Randomization will be stratified into 2 groups: 1) *de novo* AML vs. 2) all other patients.

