##### Secondary Endpoints

Endpoints for secondary objectives include: the development of proven or probable IA defined according to criteria developed by the EORTC/MSG (from which time to IA will be computed), death due to any cause (from which time to death will be computed), the need for empiric antifungal therapy defined as the institution of antifungal therapy while a study subject is receiving prophylaxis (from which the days of empirical antifungal therapy will be computed), results from GM and beta-D glucan assays for the diagnosis of IFI or IA alone, and results of the genotyping assays for SNP analysis.

An exploratory endpoint will be the development of proven, probable or possible IFI.

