### 9.3.2 Central Committee Review

In order to ensure consistent and accurate application of the EORTC/MSG guidelines across all study patients, a Central Review Committee including Pediatric Oncologists and Pediatric Infectious Disease Specialists will be assembled. Through consensus meetings, committee members will review all data pertinent to the EORTC/MSG guidelines and determine whether a patient sustained a possible, probable or proven IFI or IA infection during the study period. The following data for each study patient will be collected and available at the time of the review: pathology reports, all CT scan and MRI reports, fungal Gram stain and microbiology culture results, non-culture mycology testing results (i.e., Histoplasma urine antigens, cryptococcal CSF and serum antigens), ophthalmology exams, bronchoscopy reports, and dosing and duration of steroid exposures.

All reviewers will be blinded to the patient's antifungal exposures in order to limit any bias in determining the primary and secondary endpoints.

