### 13.6 Methodology to Identify IFI and IA

The EORTC/MSG guidelines incorporate clinical, microbiologic, histopathologic, and radiographic data for classification of proven or probable IFI or IA. Therefore, in order to establish these diagnoses, the following data will be obtained (according to the IFI checklist (Section 10.2): pathology reports (including autopsy reports), CT scan and MRI reports, fungal gram stain and microbiology culture results, non-culture mycology testing results (i.e. histoplasma urine antigens, cryptococcal CSF and serum antigens), ophthalmology exams, and bronchoscopy reports. An independent data review committee including infectious disease and oncology experts who are unaware of treatment assignments will review and classify all cases of fungal infection according to the consensus criteria of the EORTC/MSG.

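### Sections 9.3.2 and 10.2 contradict each other on what the blinded IFI committee receives and which categories it assigns, and no section says whether local galactomannan and beta-D glucan results reach it

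*Combined protocol and SAP*

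**What the plan says.** **What the committee receives.** Section 9.3.2 states that data "for each study patient will be collected and available at the time of the review: pathology reports, all CT scan and MRI reports", followed by cultures, non-culture mycology, ophthalmology, bronchoscopy and steroid exposure. Section 10.2 lists the same document types but has sites submit them "at the end of each course of protocol therapy, only if they were performed to investigate an IFI according to local physician discretion". Section 13.6 repeats the list and refers to the 10.2 checklist. Steroid data are entered electronically, outside the filter. For cultures, eye examinations and bronchoscopies, 10.2 asks for negative as well as positive findings.

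**What the committee classifies.** Under 9.3.2 it must "determine whether a patient sustained a possible, probable or proven IFI or IA infection during the study period". Under 10.2 it "will review and classify all cases of proven/probable IFI by EORTC/MSG". Under 13.6 it will "review and classify all cases of fungal infection according to the consensus criteria of the EORTC/MSG". Section 9.3.1 adds: "An exploratory endpoint will be the development of proven, probable or possible IFI".

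**Who knows the arm.** "This is a randomized open-label trial" (Section 9.1). Sections 9.3.2 and 10.2 blind the reviewers only.

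**GM and BDG.** The non-culture mycology item in 9.3.2, 10.2 and 13.6 is followed by an i.e. that names only Histoplasma and cryptococcal antigens. Appendix II counts GM and BDG as mycological criteria, and a case with host and clinical criteria but no mycological criterion is only possible. Section 13.1.8 expects some physicians to order these tests locally, keeps the local results out of the assay analysis, and does not say whether the committee sees them.

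**The concern.** Central blinded review is the plan's protection against assessment bias in an open-label trial. It protects only what reaches the committee. Under 9.3.2 nothing is filtered. Under 10.2 a chest CT ordered for another stated reason stays at the site, even if it shows a sign that Appendix II accepts as a clinical criterion. A site cannot satisfy both sections, and 10.2 is the one written as an instruction to sites.

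The categories matter because the line between possible and probable is the line between a non-event and an event in the primary analysis, and because the exploratory endpoint needs the possible cases.

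GM and BDG raise a problem whichever way the silence is resolved. If local results are not sent, a case whose only mycological evidence is one of these tests is classed as possible and lost from the primary endpoint. If they are sent, the gold standard used in Section 13 to judge GM and BDG would partly consist of GM and BDG.

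**Working it through.** **Step 1. Passages side by side.**

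| | 9.3.2 | 10.2 | 13.6 |
|---|---|---|---|
| Patients | each study patient | those with an IFI work-up | as 10.2 |
| CT/MRI reports | all | only if done to investigate an IFI | as 10.2 |
| Local judgement | none | yes | as 10.2 |
| Categories | possible, probable, proven | proven/probable | all fungal infection |
| GM/BDG named | no | no | no |

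On receipt the conflict is between 9.3.2 and 10.2; 13.6 follows 10.2. On categories all three differ. The discretion in 10.2 can attach to ordering the test or to sending it. On either reading the condition that the test was done to investigate an IFI is narrower than all CT and MRI reports for every patient.

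**Step 2. Events on which the endpoint rests.** Inputs from 9.3.3: 275 per arm, 8% versus 2% at T = 5 months, 35% censored by 5 months, failure and censoring both exponential.

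- Hazards per month: λ = −ln(1 − p)/5, giving 0.01668 (fluconazole) and 0.00404 (caspofungin); censoring λc = −ln(0.65)/5 = 0.08616.
- Hazard ratio: ln(0.98)/ln(0.92) = 0.242, which reproduces the plan's 0.24.
- Probability of an observed event: λ/(λ + λc) × [1 − exp(−5(λ + λc))], where the exponential is (1 − p) × 0.65.
- Fluconazole: 0.1622 × (1 − 0.598) = 0.0652; × 275 = 17.9.
- Caspofungin: 0.0448 × (1 − 0.637) = 0.0163; × 275 = 4.5.
- Total: 22.4.

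**Step 3. How many events must be lost.** With equal arms and few events the log rank statistic is close to Z = (a − b)/√(a + b), where a and b are the fluconazole and caspofungin events. Two critical values are used: 1.96, ignoring interim looks, and 2.06. The latter assumes looks at one third, two thirds and all of the information, with the spending function in 9.3.5 (not fully legible in the text) read as αt². This gives boundaries 2.77, 2.35 and 2.06 (final nominal p = 0.039).

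| Split | Z | Above 1.96 | Above 2.06 |
|---|---|---|---|
| 18 vs 4 | 2.98 | yes | yes |
| 13 vs 4 | 2.18 | yes | yes |
| 12 vs 4 | 2.00 | yes | no |
| 11 vs 4 | 1.81 | no | no |
| 18 vs 5 | 2.71 | yes | yes |
| 14 vs 5 | 2.065 | yes | yes (boundary 2.062) |
| 13 vs 5 | 1.89 | no | no |

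From 18 vs 4, significance goes after 6 lost fluconazole events (at 2.06) or 7 (at 1.96). From 18 vs 5 it goes after 5 at either value. Near the boundary one suffices: 13 vs 4 crosses 2.06 and 12 vs 4 does not.

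**Step 4. What cannot be computed.** The documents give no share of true cases that would fail the 10.2 condition, by arm or overall, and no count of cases resting on GM or BDG alone. No bias or power loss is therefore estimated.

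**The case against.** The best defence is that discretion in 10.2 most naturally describes clinical practice: tests are done when the treating physician suspects fungal infection, and no committee can review a scan that was never ordered. Section 10.2 also guards against selective sending by asking for negative cultures, eye examinations and bronchoscopies. A patient who truly has proven or probable IFI will usually have been worked up for it. All of this stands and limits the exposure to reports ordered for another stated reason. It does not reconcile the two sections, because 9.3.2 promises those reports too.

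On possible cases, 9.3.2 already assigns them and 10.2 does not forbid it. A reader might infer that the exploratory endpoint has no adjudication; the documents do not support that. The wording needs aligning.

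On GM and BDG, 9.3.2 speaks of all data relevant to the EORTC/MSG guidelines, which may well cover them. Section 13.1.8 also records whether local testing was done, and 13.8.4 plans an analysis excluding patients with a locally available result. So a reader should not conclude that these results are barred from the committee or that local testing was overlooked. But none of these provisions says what the committee receives.

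A reader might also infer that infections after protocol therapy go unreported, because the Section 7.1 footnote asks for uploads "at the end of each course of protocol therapy. See Section 10.2 for further details". That is not supported: the 7.1 table adds an end-of-therapy checklist, 8.1 and 8.3 require follow-up after therapy stops, and Section 12 refers to a form submission schedule that is not reproduced here.

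**Conclusion.** The contradiction between 9.3.2 and 10.2 is established from the text, concerns the primary endpoint and should be fixed. As 10.2 stands, an unblinded local judgement comes before the blinded review. The differing categories and the silence on GM and BDG should be settled in the same edit.

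It is tempting to go further and say that the comparison is biased towards one drug. The documents do not support that: differential submission is possible, but neither its size nor its direction can be derived. At the planned split the result would survive the loss of up to 4 fluconazole events; a result close to the boundary could turn on one. These counts rest on the event rates and censoring in 9.3.3, the approximate Z above, losses in the fluconazole arm only, and, for the 2.06 boundary, the stated reading of 9.3.5.

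**What to change.** **(a) One submission rule and one set of categories.** In 10.2 replace the local-discretion condition with an arm-neutral rule consistent with 9.3.2. From randomization until the criteria in 8.3 or 8.2 are met, sites send all CT and MRI reports; every fungal-positive pathology, culture, antigen or bronchoscopy result whatever the reason for the test; and, as now, the negative results from IFI work-ups. State in 10.2 and 13.6, as in 9.3.2, that the committee assigns possible, probable and proven. For submissions after protocol therapy, a cross-reference to the Section 12 schedule is enough if that schedule already requires them.

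**(b) GM and BDG.** Name local GM and BDG results in the lists in 9.3.2 and 10.2 for the primary endpoint. For the Section 13 accuracy analyses, use a classification in which neither test counts as the mycological criterion.

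**Cost.** A text amendment to 9.3.2, 10.2 and 13.6, with a sentence in Section 13 on the second classification. Sites upload more existing reports, which runs against the aim in 10.2 of limiting their work, and the committee classifies a second time the few cases that rest on GM or BDG alone. The change does not recover infections for which no test was ordered.

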## 11.0 ADVERSE EVENT REPORTING REQUIREMENTS

### 11.1 Purpose

Adverse event data collection and reporting, which are required as part of every clinical trial, are done to ensure the safety of patients enrolled in the studies as well as those who will enroll in future studies using similar agents.

### 11.2 Determination of Reporting Requirements

Reporting requirements may include the following considerations: 1) the characteristics of the adverse event including the *grade* (severity); 2) the *relationship to the study therapy* (attribution); and 3) the *prior experience* (expectedness) of the adverse event.

Commercial agents are those agents not provided under an IND but obtained instead from a commercial source. In some cases an agent obtained commercially may be used for indications not included in the package label. In addition, NCI may on some occasions distribute commercial supplies for a trial. Even in these cases, the agent is still considered to be a commercial agent and the procedures described below should be followed.

Determine the prior experience Expected events are those that have been previously identified as resulting from administration of the agent. An adverse event is considered *unexpected*, for reporting purposes only, when either the type of event or the severity of the event is not listed in:

- ***the current known toxicities for each commercial agent as provided in the Drug Information for Commercial Agents Used by the Children's Oncology Group posted on the COG website; or***
- ***the drug package insert.***

#### Secondary Malignancy

A ***secondary malignancy*** is a cancer caused by treatment for a previous malignancy (eg, treatment with investigational agent/intervention, radiation or chemotherapy). A metastasis of the initial neoplasm is not considered a secondary malignancy.

All secondary malignancies that occur following treatment need to be reported via CTEP-AERS. Three options are available to describe the event:

- Leukemia secondary to oncology chemotherapy
- Myelodysplastic syndrome
- Treatment related secondary malignancy

### 11.3 Reporting of Adverse Events for Commercial Agents - via CTEP-AERS

Expedited AE reporting must use CTEP-AERS (Adverse Event Expedited Reporting System), accessed via <https://eapps-ctep.nci.nih.gov/ctepaers>

Commercial reporting requirements are provided in Table B. The commercial agent(s) used in this study are listed in the front of this protocol immediately following the Study Committee roster.

- COG requires the CTEP-AERS report to be submitted **within 7 calendar days** of learning of the event.
- Use the NCI protocol number and the protocol-specific patient ID provided during trial registration on all reports.

**CTCAE term (AE description) and grade:** The descriptions and grading scales found in the NCI Common Terminology Criteria for Adverse Events (CTCAE) version 4 will be utilized for AE reporting and are located on the CTEP website at:

[http://ctep.cancer.gov/protocolDevelopment/electronic\\_applications/ctc.htm](http://ctep.cancer.gov/protocolDevelopment/electronic_applications/ctc.htm). All appropriate treatment areas should have access to a copy of the CTCAE.

#### **Table B**

**Reporting requirements for adverse events experienced by patients on study who have NOT received any doses of an investigational agent on this study.**

**CTEP-AERS Reporting Requirements for Adverse Events That Occur During Therapy With a Commercial Agent or Within 30 Days**

Attribution	Grade 4		Grade 5
	Unexpected	Expected	
Unrelated or Unlikely			CTEP-AERS
Possible, Probable, Definite	CTEP-AERS		CTEP-AERS
 This includes all deaths within 30 days of the last dose of treatment with a commercial agent, regardless of attribution. Any death that occurs more than 30 days after the last dose of treatment with a commercial agent which can be attributed (possibly, probably, or definitely) to the agent and is not due to cancer recurrence must be reported via CTEP-AERS			

**11.4 Routine Adverse Event Reporting**

**Note:** The guidelines below are for routine reporting of study specific adverse events on the COG case report forms and do not affect the requirements for **CTEP-AERS** reporting.

The NCI defines both routine and expedited AE reporting. Routine reporting is accomplished via the Adverse Event (AE) Case Report Form (CRF) within the study database. For this study, routine reporting will include all toxicities reported via CTEP-AERS and all Grade 4 and higher non-hematological Adverse Events.

**12.0 RECORDS AND REPORTING**

See the Case Report Forms posted on the COG web site with each protocol under “*Data Collection/Specimens*”. A submission schedule is included.

**12.1 CDUS**

This study will be monitored by the Clinical Data Update System (CDUS). Cumulative CDUS data will be submitted quarterly to CTEP by electronic means. Reports are due January 31, April 30, July 31 and October 31. This is not a responsibility of institutions participating in this trial.

### **13.0 PROSPECTIVE EVALUATION OF GALACTOMANNAN AND (1→3) BETA-D GLUCAN ASSAYS AS DIAGNOSTIC TOOLS FOR INVASIVE FUNGAL INFECTION IN CHILDREN WITH ACUTE MYELOID LEUKEMIA RECEIVING FUNGAL PROPHYLAXIS.**

#### **13.1 Sample Collection and Testing Procedures (These studies are optional)**

##### 13.1.1 Sample submission

At the time of enrollment, if a new patient has consented to the optional galactomannan and beta-D glucan study, a sample collection kit will be automatically express delivered to the treating institution. If the kit is not received within 48 hours of enrollment, please contact [name] at MiraVista [contact] x451) as soon as possible to prevent any further delays. The kit contains special vials that are mandatory for specimen collection. Alternative specimen vials should never be used as they may contribute to false results.

##### 13.1.2 Sample Collection

Whole blood samples will be collected twice weekly during the period of neutropenia (until ANC > 100-500/ $\mu$ L). It is suggested that specimens be obtained on Mondays and Thursdays but other days are acceptable if more convenient. A minimum of 2 days should separate each specimen collection.

In order to perform both assays on a single specimen (Platelia™ Aspergillus EIA and Fungitell® beta-D glucan assay), collect 5 mL of whole blood in a gold top serum-separator tube (provided by MiraVista) and label with the site number, COG ID number, and date (labels will be provided with the sample shipping kit). Although the above volume of blood testing will likely represent a small fraction of the blood testing performed during the period of 1 week, it may result in an important increase in certain patients (i.e., smaller children or anemic children). Therefore, we have set the following maximum limits per kilogram for blood draws related to this ancillary study: 3 mL of blood/kg body weight in an 8 week period.

